4. LIST OF ABBREVIATIONS AND DEFINITIONS OF TERMS

Table 6: Abbreviations and Specialist Terms

Abbreviation	Definition
AE	adverse event
████████	████████
BMI	body mass index
CS	clinically significant
COVID-19	coronavirus disease 2019
C-SSRS	Columbia-Suicide Severity Rating Scale
ECG	electrocardiogram
eCRF	electronic case report form
EOS	End of Study
EOT	End of Treatment
ESS	Epworth Sleepiness Scale
ET	essential tremor
GABA _A	γ-aminobutyric acid-gated chloride channel
GCP	Good Clinical Practice
ICF	informed consent form
ICH	International Council for Harmonisation
ID	identification
IEC	Independent Ethics Committee
IP	investigational product
IRB	Institutional Review Board
IRT	interactive response technology
NCS	not clinically significant
████████	████████
████████	████████
████	████
PWC-20	20-item Physician Withdrawal Checklist
QTcF	QT corrected according to Fridericia's formula
SAP	statistical analysis plan
SAE	serious adverse event
SUSAR	suspected unexpected serious adverse reaction

Abbreviation	Definition
TEAE	treatment-emergent adverse event
TETRAS	The Essential Tremor Rating Assessment Scale
WOCBP	woman of childbearing potential

5. INTRODUCTION

SAGE-324 is a positive allosteric modulator of A-type γ -aminobutyric acid-gated chloride channel (GABA_A) receptors, the major class of inhibitory neurotransmitter receptors in the brain. SAGE-324 is planned to be evaluated for multiple indications affected by activity at the GABA_A receptor, including essential tremor (ET).

Clinical studies of SAGE-324 in healthy adults and in adults with ET, in addition to preclinical studies of SAGE-324, are detailed in the SAGE-324 investigator's brochure as well as a detailed description of the chemistry, pharmacology, efficacy, and safety of SAGE-324.

ET is a common, permanently debilitating, neurologically determined movement disorder characterized by involuntary rhythmic oscillation of a body part due to intermittent muscle contractions. This shaking typically occurs during voluntary movement (ie, when not at rest), thus interfering with fine motor skills associated with daily activities (Olanow 2008, Deuschl 2011, Hopfner 2016, NIH 2019). Although the pathophysiology and etiology of ET is not fully understood, it is postulated that approximately 50% of ET patients feature an autosomal dominant pattern of familial inheritance and that noninherited cases may have toxin-based or other causality (Olanow 2008, Hopfner 2016). ET is the most common movement disorder in the US and worldwide, with prevalence estimated to be approximately 2.2% of the population, representing a substantial societal medical burden with over an estimated 7 million ET patients in the US alone (Louis 2014).

In general, active tasks of daily life are adversely impacted by ET, including but not limited to speech, handwriting, household tasks, and occupational demands, contributing negatively to psychosocial well-being, general anxiety, and overall quality of life (Koller, 1989). Although benign in terms of its effect on life expectancy, ET is a progressive neurodegenerative condition whose symptoms are typically disabling, often forcing patients to change jobs or seek early retirement (Zappia, 2013). In some cases, serious disability may ensue.

Current first-line therapies, propranolol and primidone, are the most commonly used medications for the treatment of ET. These therapies reduce tremors by >50% in 40% of people (Koller 1994), while up to 30% of patients do not respond to first-line therapy or experience intolerable adverse effects (Koller 1989). The only Food and Drug Administration-approved pharmacological treatment for ET is propranolol, a β -adrenergic receptor antagonist. Because of its non-selective mechanism of action, not all individuals with ET are able to take propranolol due to contraindications such as asthma, heart failure, and diabetes (propranolol Prescribing Information). In addition, propranolol is not always well tolerated, mainly due to fatigue and similar adverse reactions, as well as rare serious adverse reactions (Olanow 2008, Wyeth 2010). Secondary pharmacologic approaches to the treatment of ET have included off-label use of anticonvulsants with limited GABA activity (eg, topiramate, gabapentin) and the use of alcohol (Rajput 2014). Notably, tolerability is a key limiting factor of propranolol, primidone, and similar therapies utilized by ET patients.

Five clinical pharmacology studies (324-CLP-101, 324-CLP-102, 324-CLP-104, 324-CLP-105, and 324-CLP-106) and 1 efficacy study (324-ETD-201) are complete. The results of these clinical studies suggest that SAGE-324 may safely ameliorate symptoms in patients suffering from ET.

With a GABA_A receptor-based mechanism of action featuring positive allosteric modulation capability, SAGE-324 represents a novel approach to the treatment of ET, which may help address the unmet medical need of the ET population, warranting further study of SAGE-324 as a potential treatment for this common movement disorder.

This open-label safety study is designed to collect long-term safety and tolerability data in participants with ET and will be initiated at the highest dose of SAGE-324 being assessed in the dose-ranging study 324-ETD-202.

5.1. Dose Justification

The present study (324-ETD-303) is a long-term, open-label study to evaluate the safety and tolerability of SAGE-324 in participants with ET. The dose selected for the study is the highest dose that is included in the dose-ranging study 324-ETD-202. Once the dose-ranging study is completed and a dose or doses are selected for inclusion in pivotal studies, this protocol will be amended to employ the highest of the doses included in the pivotal studies. This is in line with the ICH E1A guideline, requiring exposure at the dosage level(s) intended for clinical use.

In order to mitigate the adverse event (AE) of somnolence that was observed in study 324-ETD-201, nighttime dosing will be employed as well as an up-titration to the 60-mg dose (Section 7.3). Up-titration is a standard practice that is designed to allow participants to accommodate to the AE as plasma concentrations rise more slowly than they would if the target dose was administered from the start. Participants will be allowed to down-titrate at any time if intolerable AEs occur.

5.2. Benefit/Risk Assessment

Potential benefits and risks anticipated in this study are based on available data from 5 completed clinical pharmacology studies (324-CLP-101, 324-CLP-102, 324-CLP-104, 324-CLP-105, and 324-CLP-106) and 1 completed efficacy study (324-ETD-201), as well as toxicology studies of SAGE-324. Available nonclinical and clinical data are summarized in the SAGE-324 investigator's brochure.

Based on the mechanism of action of SAGE-324 and the results of completed nonclinical and clinical studies of SAGE-324, participants receiving SAGE-324 may have tremor reduction and improved quality of life.

In a Phase 2, randomized, double-blind, placebo-controlled study (324-ETD-201), a statistically significant treatment difference for SAGE-324 versus placebo was observed for the primary efficacy endpoint (-1.07; 95% confidence interval: -2.14 to -0.00; $p = 0.0491$), and clinically meaningful effects were reported by participants. In addition, the sensitivity analyses showed consistency of the primary endpoint results, and subgroup analyses demonstrated a treatment difference for SAGE-324 versus placebo in most subgroups. Also, a statistically significant reduction from baseline in The Essential Tremor Rating Assessment Scale (TETRAS) Performance Subscale item 4 upper limb tremor score at Day 29 was observed in a population with baseline upper limb tremor score of ≥ 12 ($p = 0.0066$). Overall, the primary endpoint analyses have demonstrated potentially positive and therapeutic effects of SAGE-324 in participants suffering from ET.

In Study 324-ETD-201, treatment-emergent adverse events (TEAEs) of somnolence, feeling of relaxation, and dizziness have been most frequently reported. Most of the somnolence, dizziness, and feeling of relaxation events were mild or moderate. There were 2 serious adverse events (SAEs) of mental status changes that were considered related to investigational product (IP) by the investigators. Some of the reported events required dose reduction or study discontinuation, but all events resolved without sequelae or requiring treatment.

In Study 324-ETD-201, participants were administered 60 mg SAGE-324 in the morning without prior up-titration. Participants in the current study will be dosed at nighttime and the dose will be titrated up to 60 mg in 15 mg steps in order to mitigate the most commonly reported AE of somnolence in previous studies. Study participants will be closely monitored during scheduled visits, via phone calls in between clinic visits (as needed), or more frequently for AE monitoring as appropriate.

6. STUDY OBJECTIVES AND ENDPOINTS

Objectives	Endpoints
Primary	

• To assess the long-term safety and tolerability of SAGE-324	
• Incidence of TEAEs
Secondary	
• To assess the long-term effect of SAGE-324 on other safety parameters• Change from baseline in vital signs, electrocardiogram (ECG), and clinical laboratory parameters, Epworth Sleepiness Scale (ESS) and Columbia-Suicide Severity Rating Scale (C-SSRS) responses• Physician Withdrawal Checklist (PWC-20) scores

[figure not shown]
7. INVESTIGATIONAL PLAN

7.1. Overall Study Design

This is an open-label study to evaluate the long-term safety and tolerability of SAGE-324 in participants with ET who have completed the planned End of Treatment (EOT) Visit and who were not early terminated during the planned Treatment Period in another SAGE-324 study.

The study design is presented in Figure 2.

Figure 2: Study Design

This study includes a Screening Period of up to 28 days, a Treatment Period with weekly outpatient visits for the first 8 weeks, outpatient visits on Weeks 10, 12, 16, 20, and 24, and quarterly outpatient visits thereafter to the end of dosing, and a 14-day Follow-up Period. After providing informed consent, participants will undergo screening assessments as outlined in [Table 2](#) to determine eligibility.

Screening Period:

The Screening Period begins with the signing of the informed consent form (ICF). Eligible participants will complete additional eligibility and baseline assessments, as specified in the Schedule of Assessments ([Table 2](#)).

At the discretion of the investigator, clinical laboratory assessments from a completed SAGE-324 study may be used to determine eligibility for this study if taken within 28 days of Day 1.

Open-label Treatment Period:

Starting on Day 1, participants will self-administer on an outpatient basis a single dose of SAGE-324 once daily in the evening before bed, with a snack if bedtime is not within 2 hours of the evening meal. Guidance on suitable snacks will be provided.

During the Treatment Period, participants will return to the study center for safety, tolerability, [REDACTED] as specified in [Table 2](#), [Table 3](#), and [Table 4](#). In addition, safety phone call study visits will be conducted as deemed appropriate by the investigator to review the current status of the participant. Participants will be trained on the use of software applications and devices necessary to complete questionnaires and/or self-rated study assessments.

Participants should gain experience with the study drug to see how it affects them before engaging in potentially hazardous activities requiring mental alertness, such as driving. If participants experience any sleepiness, dizziness, or feelings of relaxation, or have other sedative effects, they should not engage in potentially hazardous activities requiring mental alertness, such as driving, until any sleepiness/sedative effects from the study drug have dissipated. This is important because study participants may not be able to judge how these sedative effects will affect their ability to perform potentially hazardous activities requiring mental alertness, including driving.

The Treatment Period will continue for as long as the participant continues to self-administer SAGE-324 or until marketing authorization, projected to be up to approximately 5 years.

Follow-Up Period:

Follow-up visits will be conducted on an outpatient basis when participants have completed the Treatment Period. Participants will continue to complete questionnaires as indicated in [Table 4](#) and will return to the clinic 3 (± 3) days after the last dose of SAGE-324 for safety, tolerability, [REDACTED] at the End of Treatment (EOT) Visit. Participants will return to the study center for an End of Study (EOS) Visit, 14 (± 3) days after the last dose of SAGE-324.

7.2. Number of Participants

It is estimated that approximately 750 participants will be dosed in and complete the study to contribute exposures to the safety database for SAGE-324 in accordance with International Council for Harmonisation (ICH) E1a guidelines.

[REDACTED]

7.3. Treatment Assignment

SAGE-324 will be self-administered orally once daily in the evening before bed, with a snack if bedtime is not within 2 hours of the evening meal.

Participants will self-administer 15 mg SAGE-324 on Day 1 to Day 14, 30 mg on Day 15 to Day 28, 45 mg on Day 29 to Day 42, and then 60 mg daily starting on Day 43.

7.4. Dose Adjustment Criteria

If a participant experiences AEs at any time during the Treatment Period that are considered by the investigator to be related to the IP and not tolerable, the investigator may reduce the dose of

IP in 15 mg decrements, including during the initial dose escalation period. Administration of IP will be interrupted for 3 to 8 days before the initiation of the reduced dose.

7.5. Criteria for Study Termination

Sage Therapeutics may terminate this study or any portion of the study at any time for safety reasons including the occurrence of AEs or other findings suggesting unacceptable risk to participants, or for administrative reasons. In the event of study termination, Sage Therapeutics will provide written notification to the investigator. Investigational sites must promptly notify their institutional review board (IRB)/independent ethics committee (IEC), where required, and initiate withdrawal procedures for participating participants.

7.6. End of Study Definition

The end of the study is defined as the date of the last visit of the last participant in the study. A participant is considered to have concluded the study if he/she has completed dosing and completed the EOS Visit as per the Schedule of Assessments ([Table 4](#)) or is lost to follow-up.

8. SELECTION AND WITHDRAWAL OF PARTICIPANTS

8.1. Participant Inclusion Criteria

Participants are eligible to be included in the study if all of the following criteria are met:

1. Participant has signed an ICF before any study-specific procedures are started.
2. Participant is ambulatory and is 18 to 80 years of age, inclusive, at the time informed consent is obtained.
3. Participant is in good physical health and has no clinically significant findings (excluding ET) that may impact their ability to participate in the study, as determined by the investigator, on physical examination, 12-lead ECG, or clinical laboratory tests.
4. Participant has a clinician-confirmed diagnosis of ET in compliance with all the following criteria:
 - a. Duration of at least 3 years
 - b. Absence of other neurological signs, such as dystonia, ataxia, parkinsonism, task- and position-specific tremors, sudden tremor onset, or evidence of stepwise deterioration of tremor
 - c. Absence of historical or clinical evidence of tremor with psychogenic origin (including, but not limited to, eating disorders and major depression)
5. Participant has completed the planned End of Treatment (EOT) Visit and was not early terminated during the planned Treatment Period in another SAGE-324 study.
6. Female participant agrees to use at least one method of highly effective contraception as listed in Section [9.2.5](#) during participation in the study and for 30 days following the last dose of study drug, unless she is postmenopausal (at least 12 months of spontaneous amenorrhea without an alternative medical cause, with confirmatory follicle stimulating hormone [FSH] >40 mIU/mL), or surgically sterile (bilateral oophorectomy, hysterectomy, and/or bilateral salpingectomy), or does not engage in sexual relations which carry a risk of pregnancy (does include abstinence).
7. Male participant agrees to use an acceptable method of effective contraception for the duration of the study and for 13 weeks after receiving the last dose of study drug, unless the participant does not engage in sexual relation(s) which carry a risk of pregnancy. Acceptable methods of effective contraception are listed in Section [9.2.5](#).
8. Male participant is willing to abstain from sperm donation for the duration of the study and for 13 weeks after receiving the last dose of study drug.

9. Participant is willing to limit use of alcohol to 2 units per day for males and 1 unit per day for females starting at least 1 week prior to Day 1 and through the EOS Visit.
A unit of alcohol is defined as: 12 ounces of regular beer, 5 ounces of wine, or 1.5 ounces of distilled spirits.
Participant will limit alcohol use to at least 2 hours before self-administration of IP in the evening.
Participant will not use alcohol starting 24 hours prior to scheduled in-clinic study visits until all assessments have been completed.
10. Participant is willing to maintain prestudy consumption of products that contain nicotine starting at least 1 week prior to Day 1 and through EOS Visit.

8.2. Participant Exclusion Criteria

Participants are excluded from the study if any of the following criteria apply:

1. Participant has presence of alcohol withdrawal state.
2. Participant has had direct or indirect injury or trauma to the nervous system within 3 months before the onset of tremor.
3. Participant is taking and unable to discontinue the use of primidone at least 7 days prior to administration of the first dose of SAGE-324. [REDACTED]
[REDACTED]
4. Participant has a history (within 3 years of Screening) or ongoing oncologic disease, excluding skin cancers (squamous or basal cell carcinoma) for which treatment has been completed and any carcinoma in situ.
5. Participant has an ongoing clinically relevant medical or psychiatric condition that, in the judgment of the investigator, is not well managed and poses a risk for participation in the study.
6. Participant has history of substance dependence and/or abuse prior to Screening, has a positive screen for drugs of abuse at Screening or predose on Day 1 (unless prescribed). Participants with nicotine use disorder that impacts their tremor are excluded.
7. Participant has a known allergy to SAGE-324 or any excipient.
8. Female participant has a positive pregnancy test or confirmed pregnancy or is breastfeeding.
9. Participant has had exposure to another investigational drug or device within 30 days or 5 half-lives of the other investigational drug, whichever is longer, prior to the Day 1 visit and for the duration of the study.
10. Participant has a history of suicidal behavior within 2 years or answers “YES” to questions 3, 4, or 5 on the C-SSRS at Screening or at Day 1 or is currently at risk of suicide in the opinion of the investigator.
11. Participant has night shift work.

12. Participant has any condition or comorbidity that in the opinion of the investigator would limit or interfere with the participant's ability to complete or partake in the study.
13. Participant is unwilling or unable to comply with study procedures and required training.
14. Participant has used any known moderate or strong cytochrome P450 3A4 inhibitors and/or inducers within 14 days or 5 half-lives (whichever is longer) prior to Day 1 or consumed grapefruit juice, grapefruit, Seville oranges, or St. John's Wort or products containing these within 30 days prior to Day 1 and is unwilling to refrain from taking these medications or foods for the duration of dosing. Use of mild cytochrome inhibitors and/or inducers may be permitted.
15. Participant is investigative site personnel or a member of their immediate families (spouse, parent, child, or sibling whether biological or legally adopted).

8.3. Screen Failures

Screen failures are defined as participants who consent to participate in the clinical study but failed one or more eligibility criteria and are not subsequently enrolled in the study. A minimal set of screen failure information will be collected, including demography, screen failure details, eligibility criteria, and any SAE.

8.4. Investigational Product Discontinuation and End of Study Activities

8.4.1. Investigational Product Discontinuation

A participant may withdraw from the study at any time at his/her own request for any reason. The investigator may discontinue a participant from the study and/or from IP for safety, behavioral, compliance, or administrative reasons.

The reason for IP discontinuation and/or the reason for termination from the study must be documented in the participant's source documentation and recorded in the participant's electronic case report form (eCRF).

The investigator must notify the sponsor and/or the medical monitor when a participant stops participation in the study for any reason.

8.4.2. End of Study Activities

The duration of participation in this study is dictated by the duration of continued administration of IP. If the IP is permanently discontinued, two further study visits will be conducted: one approximately 3 days after IP discontinuation (EOT Visit) and another approximately 14 days after IP discontinuation (EOS Visit). If the participant does not attend the EOS Visit, they will be considered to be lost to follow-up.

If the participant withdraws consent for disclosure of future information, the sponsor will retain and continue to use any data collected before such a withdrawal of consent.

If a participant withdraws from the study, he/she may request destruction of any samples taken and not tested, and the investigator must document this in the site study records.

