8.4.3. Lost to Follow-up

A participant will be deemed lost to follow-up after 3 unsuccessful documented attempts to contact the participant.

[REDACTED]

[REDACTED]

[REDACTED]

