8.2. Background Characteristics

8.2.1. Participant Disposition

The summary of disposition will use the All Participants Set and include number of participants who were screened, screen failed, successfully screened but did not dose, and successfully screened and dosed (overall and by previous study participation), and, using the number of participants who successfully screened and dosed as the denominator, the number and percentage of participants who completed treatment, who discontinued treatment (overall, by dose level, and by primary reason for discontinuing treatment), who completed the study, and who discontinued the study (overall and by primary reason).

If a participant is rescreened because he/she has been a screen failure the first time, the status of the participant will be determined from the second screening. In the count of screened participants, such a participant will be counted only once.

A completer of the study is a participant with the study completion question answered 'Yes' on the End of Study / Study Disposition CRF page. A completer of treatment is a participant with the treatment completion question answered 'Yes' on the IP Completion / Discontinuation CRF page. The primary reason for discontinuing the study is provided in the respective CRF page.

The number of participants in each of the analysis sets will also be summarized and presented, using the All Participants Set. The reasons for participants being excluded from each analysis set will be listed (using All Participants) but not summarized.

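### Protocol 8.4.2 counts every missed EOS Visit as lost to follow-up, in conflict with 8.4.3 and 8.4.1, so study-discontinuation reasons can be miscoded

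*Protocol*

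**What the plan says.** **Protocol 8.4.2 (End of Study Activities).** Two visits follow permanent discontinuation of IP, at about 3 days (EOT) and about 14 days (EOS). The section then says: "If the participant does not attend the EOS Visit, they will be considered to be lost to follow-up". It has no exception and no reference to 8.4.3.

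**Protocol 8.4.3 (Lost to Follow-up).** "A participant will be deemed lost to follow-up after 3 unsuccessful documented attempts to contact the participant".

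**Protocol 8.4.1 (Investigational Product Discontinuation).** Withdrawal is a separate way out: "A participant may withdraw from the study at any time at his/her own request for any reason". The section also says: "The reason for IP discontinuation and/or the reason for termination from the study must be documented", in source and in the eCRF.

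**Protocol 7.6 (End of Study Definition).** "A participant is considered to have concluded the study if he/she has completed dosing and completed the EOS Visit", and the only other route it names is "or is lost to follow-up".

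**SAP 8.2.1 (Participant Disposition).** The disposition summary counts participants "who discontinued the study (overall and by primary reason"). On the source of that reason: "The primary reason for discontinuing the study is provided in the respective CRF page". The SAP does not define lost to follow-up and does not rank the reasons.

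**The concern.** The protocol has two tests for the same disposition category. One is met by a single missed visit, whatever the site knows. The other needs evidence that contact has failed. A third provision asks for the true reason. Nothing visible says which of them governs when a participant misses the EOS Visit for a known reason.

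Two things are at stake.

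- **Study disposition.** In a long-term, open-label safety study, the reasons for leaving are part of the tolerability picture. If sites resolve the conflict differently, identical cases will carry different reasons in Table 14.1.1, and the SAP has no rule that would show it.
- **SAE follow-up.** Protocol 12.2.2 lists loss to follow-up among the points at which follow-up of an ongoing SAE may end. If one missed visit is enough for that status, a literal reader could end follow-up of a participant who can still be reached.

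**Working it through.** No arithmetic applies. The plan states no dropout, missed-visit or loss-to-follow-up rate, and the conflict depends on none. The check is to apply each rule to the cases that can arise.

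| Situation at the EOS Visit | 8.4.2 | 8.4.3 | 8.4.1 |
|---|---|---|---|
| Died before the visit | Lost | Not met: status known | Record death |
| Withdrew consent, no visit | Lost | Not met: status known | Record withdrawal |
| Left because of an AE, declined the visit | Lost | Not met: contact not lost | Record the AE |
| In telephone contact, skipped the visit | Lost | Not met: contact not lost | Record the reason given |
| Missed the visit, three documented attempts failed | Lost | Lost | Record loss to follow-up |
| Attended the visit | Not lost | Not lost | Record any reason for stopping |

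The rules agree in the last two rows and disagree in the first four.

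**Could 8.4.3 be a second route rather than a necessary condition?** The text permits that reading. It does not remove the problem, because 8.4.2 alone would still classify the first four rows as lost, against 8.4.1.

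**Does the rest of the protocol settle it?** No.

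- Section 12.2.2 names death and loss to follow-up as different outcomes, which argues against 8.4.2 as worded.
- Section 7.6 gives death and withdrawal no route of their own, which pushes the other way.

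**Is this superseded text?** No. The rule stands in current 8.4.2, and the Amendment 1 summary of changes describes the same rule.

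**How would it reach the results?**

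1. The site completes the study disposition CRF page, with 8.4.1 and 8.4.2 giving different answers.
2. SAP 8.2.1 takes the primary reason from that page as entered, and Table 14.1.1 reports it.
3. Separately, Protocol 12.2.5 has each AE record state whether the event led to stopping IP or leaving the study. SAP 8.4.1 builds its AE tables and listings from those records.
4. One participant can therefore appear as lost to follow-up in Table 14.1.1 and as an AE exit in Table 14.3.1.6.

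**The case against.** The strongest reply is that the protocol and SAP already contain the safeguards.

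- Section 8.4.1 comes just before the disputed sentence and is equally binding. It covers the reason for leaving the study, not only the reason for stopping IP.
- The SAP derives nothing from EOS attendance. It also takes study completers from a CRF question, so the gap in 7.6 does not change that count.
- Treatment discontinuation by primary reason is in the same disposition summary. SAP 8.4.1 tabulates TEAEs leading to IP discontinuation, TEAEs leading to study discontinuation, and TEAEs resulting in death. Appendix C adds Tables 14.3.1.5 and 14.3.1.6 and Listings 16.2.7.3 to 16.2.7.5.

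All of this stands, and it limits the consequence. It does not remove the conflict, because neither document says that 8.4.1 prevails over 8.4.2.

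Three stronger readings are tempting, and the documents do not support them.

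- **A reader might infer that known reasons are necessarily lost.** Miscoding needs a site to enter lost to follow-up despite 8.4.1. Even then, the AE record keeps its own account of why the participant left.
- **A reader might infer that a site may close participants without trying to reach them.** No passage grants that. Section 12.2.1 requires participants who stop IP for an AE to be followed until the event resolves, is stable, or is no longer clinically significant. Section 8.4.3 presupposes contact attempts. What remains is the narrower point on ongoing SAEs under 12.2.2.
- **A reader might put a number on the misclassified participants.** Any count would rest on invented rates of early stopping and missed visits. It would also include participants who cannot be reached and are correctly lost under both rules.

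Text after 8.4.3 is redacted, and a qualifier there cannot be ruled out. The contents list shows a blacked-out heading at that place, so it may be a separate section.

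**Conclusion.** The conflict is real and in current text. As worded, 8.4.2 gives a wrong disposition for participants who miss the EOS Visit and whose status is known, and it contradicts both 8.4.3 and 8.4.1.

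The reporting effect is confined to the reasons for study discontinuation in Table 14.1.1 and the matching listing, with possible disagreement between that table and the AE-based tables. Sections 8.4.2 and 12.2.2 also need to be reconciled on when follow-up of an ongoing SAE may end.

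TEAE incidence, the reasons for stopping treatment, and the AE and death tables are not directly affected. The size cannot be estimated from the documents. The conclusion assumes that no redacted text qualifies 8.4.2 and that some sites would apply that sentence literally. The point is worth correcting because the correction costs almost nothing.

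**What to change.** 1. **Protocol 8.4.2.** Replace the sentence with wording such as: *A participant who misses the EOS Visit will be contacted. Loss to follow-up is recorded only when the criterion in Section 8.4.3 is met. In every other case the known reason, such as death, adverse event or withdrawal of consent, is recorded as Section 8.4.1 requires.*
2. **Protocol 7.6.** Align the definition, so that participants who die or withdraw are not left with loss to follow-up as the only available route.
3. **CRF completion guidance.** Say that a missed EOS Visit is not in itself a reason for study discontinuation, and that a known reason takes precedence over loss to follow-up.
4. **SAP 8.2.1.** Keep the primary reason recorded on the CRF page as the source. Do not derive loss to follow-up from contact attempts: that would override the recorded reason, and neither document shows that attempts are captured in the CRF.

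The cost is one sentence, a matching edit to 7.6 in the next amendment or an administrative letter, and a line of CRF guidance. The contact attempts are ones that 8.4.3 already expects. No analysis changes.
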